## General PK Parameter Rules

- Actual sampling times will be used in the final analyses of individual PK parameters, except for non-bolus pre-dose sampling times which will be set to zero. For non-bolus, multiple dose profiles, the pre-dose time will be set to zero unless a time deviation falls outside of the protocol blood collection time window which is considered to impact PK parameter derivation.
- $C_{\max}$ ,  $C_{\max, \text{day } 2}$ ,  $C_{\max, \text{day } 3}$ ,  $t_{\max}$ ,  $t_{\max, \text{day } 2}$ ,  $t_{\max, \text{day } 3}$ , and  $t_{\text{last}}$  will be reported from observed values. On a given profile day, if  $C_{\max}$  occurs at more than one time point,  $t_{\max}$  will be assigned to the first occurrence of  $C_{\max}$ .
- AUC parameters will be calculated using a combination of the linear and logarithmic trapezoidal methods (linear-log trapezoidal rule). The linear trapezoidal method will be applied up to  $t_{\max}$  and then the logarithmic trapezoidal method will be used after  $t_{\max}$ . The minimum requirement for the calculation of AUC will be the inclusion of at least three consecutive plasma concentrations above the lower limit of quantification (LLOQ), with at least one of these concentrations following  $C_{\max}$ . AUC(0- $\infty$ ) values where the percentage of the total area extrapolated is more than 20% will be flagged. Any AUC(0- $\infty$ ) value excluded from summary statistics will be noted in the footnote of the summary table.
- Half-life ( $t_{1/2}$ ) will be calculated, when appropriate, based on the apparent terminal log-linear portion of the concentration-time curve. The start of the terminal elimination phase for each participant will be defined by visual inspection and generally will be the first point at which there is no systematic deviation from the log-linear decline in plasma concentrations. Half-life will only be calculated when a reliable estimate for this parameter can be obtained comprising of at least 3 data points. If  $t_{1/2}$  is estimated over a time window of less than 2 half-lives, the values will be flagged in the data listings. Any  $t_{1/2}$  value excluded from summary statistics will be documented in the footnote of the summary table.
- A uniform weighting scheme will be used in the regression analysis of the terminal log-linear portion of the concentration-time curve.
- The parameters based on observed last quantifiable drug concentration ( $C_{\text{last}}$ ) will be reported.

## Individual PK Parameter Rules

- Only quantifiable concentrations will be used to calculate PK parameters with the exception of special handling of certain concentrations reported below the lower limit of quantitation (BQL). Plasma concentrations reported as BQL will be set to a value of zero when all of the following conditions are met:
  - The compound is non-endogenous.
  - The samples are from the initial dose period for a participant or from a subsequent dose period following a suitable wash-out period.
  - The time points occur before the first quantifiable concentration.

- All other BQL concentrations that do not meet the above criteria will be set to missing.
- Also, where two or more consecutive concentrations are BQL towards the end of a profile, the profile will be deemed to have terminated and therefore any further quantifiable concentrations will be set to missing for the calculation of the PK parameters unless it is considered to be a true characteristic of the profile of the drug.
- For multiple-dosing data, when pre-dose concentrations are missing, the value to be substituted will be minimum observed drug concentration ( $C_{min}$ ) for the dosing interval.
- For C10 and SNAC:
  - Predose concentrations that are BLQ will be set to half the LLOQ.
  - If quantifiable predose concentrations are observed for any of the PK profile days, the postdose concentrations of the impacted PK profile day(s) will be baseline-adjusted prior to calculation of PK parameters. Baseline-adjustment will be performed by subtracting the PK profile day's quantifiable predose concentration from each postdose concentration belonging to that same PK profile day.

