### 3. Objectives and Endpoints

Objectives	Endpoints
Primary	

 
To evaluate and compare the PK of up to 3 test capsule formulations with a reference tablet formulation of LY3493269 following 3 consecutive once-daily oral doses in healthy participants
 
	
 
AUC and <math>C_{max}</math>
 

Secondary	

 
To evaluate the PK of up to 2 LY3493269 formulations when administered in a fed condition following 3 consecutive once-daily oral doses in healthy participants
 
To assess the safety and tolerability of up to 3 test capsule formulations of LY3493269 with that of a reference tablet formulation following 3 once-daily oral doses in healthy participants
 
	
 
AUC and <math>C_{max}</math>
 
TEAEs
 

Exploratory	

 
To assess PK of SNAC and C10 following oral administration in healthy participants
 
	
 
AUC and <math>C_{max}</math>
 

Abbreviations: AUC = area under the concentration versus time curve; C10 = sodium caprate;  $C_{max}$  = maximum observed drug concentration; PK = pharmacokinetics; SNAC = salcaprozate sodium; TEAE = treatment-emergent adverse event.

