## 4.2. Scientific Rationale for Study Design

The study is intended to estimate the relative oral bioavailability of various LY3493269 4-mg oral formulations with 280 mg C10 versus a LY3493269 4 mg with 300 mg SNAC oral formulation. A population of healthy participants is selected to assess the safety and tolerability of LY3493269 co-formulated with 280 mg C10 as a capsule for oral administration with an intended lower intestinal release mechanism. An LY3493269 tablet co-formulated with 300 mg SNAC will be used as the reference treatment. Using a healthy participant population mitigates possible confounding effects of comorbidities and concomitant medications. Therefore, Study GZHI provides an unbiased assessment of safety, tolerability, and PK of LY3493269 administered as oral doses.

A study design of once-daily oral dosing for 3 days will be employed to characterize oral PK behavior of LY3493269. The dosing duration of 3 days was selected after taking into consideration the following factors:

- low oral bioavailability expected from oral peptide formulations
- the exceptionally high inter- and intra-individual variabilities in oral bioavailability expected of oral peptide formulations
- the sensitivity of the bioanalytical assay, and
- once absorbed via the oral route of administration, LY3493269 systemic PK disposition should be similar regardless of route of administration, hence safety, tolerability, and PK data from past LY3493269 studies (GZHA, GZHB, GZHC, and GZHF) should be applicable to this study.

To predict the oral PK profiles for each treatment, extensive PK simulations were conducted. The PK profile following a single oral dose was deemed to be at risk of being highly variable and potentially returning lower than quantifiable concentrations at multiple time points. The simulation results did suggest that 3 days was adequate for a majority of PK profiles from participants in each treatment group to remain above the quantification limit of CCI to yield meaningful PK results. Therefore, PK exposures from a short dosing duration of 3 days from this study are not expected to reach steady state for the respective doses.

Strict oral administration conditions such as controlling the duration of fasting before and after dosing and water volume for oral administration of LY3493269 will be imposed. These are necessary to reduce any potential variability arising from oral administration conditions that may affect oral bioavailability of LY3493269.

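### C10 samples below quantification before capsule release have no rule of their own; the general rule makes them missing on Days 2 and 3, and possibly Day 1, which distorts the exploratory C10 AUC

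*SAP*

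**What the plan says.** Under Individual PK Parameter Rules, SAP 10.3.1 sets a BQL concentration to zero only when three conditions hold together. The first is that the analyte is not an endogenous substance. The second concerns the dosing period: "The samples are from the initial dose period for a participant or from a subsequent dose period following a suitable wash-out period". The third is that the sample was drawn earlier than any quantifiable one.

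For everything else: "All other BQL concentrations that do not meet the above criteria will be set to missing".

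C10 and SNAC have their own bullets, but these deal only with predose samples: "Predose concentrations that are BLQ will be set to half the LLOQ", and a quantifiable predose value is subtracted from that day's postdose values. Under General PK Parameter Rules, AUC uses a linear-log trapezoid: "The linear trapezoidal method will be applied up to" tmax, with the logarithmic method after it.

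Protocol 4.2 describes the C10 capsule as one "with an intended lower intestinal release mechanism", and Protocol 4.3 calls it enteric. The Schedule of Activities samples C10 at predose, every half hour to 3 h, then at 4, 5, 6, 8, 9, 10, 12 and 14 h on Days 1 and 3. On Day 2 it samples at predose, 1, 2, 3, 4, 8 and 14 h. AUC is an endpoint of the exploratory objective "To assess PK of SNAC and C10 following oral administration in healthy participants".

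**The concern.** A capsule meant to release in the lower intestine should give some early postdose samples with no measurable C10. Those samples are informative: they show that absorption has not begun. If they are dropped, the predose value (half the LLOQ at time zero) is joined by a straight line to the first quantifiable sample. The calculation then credits exposure to a period in which the assay found none. The added area grows with the lag.

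At stake are C10 AUC and the parameters derived from it. One of these is the accumulation ratio R_A, which SAP 10.3.1 bases on AUCτ of Profile Days 1 and 3 and lists for C10 as well as for LY3493269.

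**Working it through.** **Step 1: which samples become missing.** The SAP does not say whether C10 is endogenous, and it does not define a dose period for three consecutive daily doses. Taking the possible readings in turn for postdose lag samples:

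| Reading | Day 1 | Days 2 and 3 |
|---|---|---|
| C10 endogenous | missing (first condition fails) | missing |
| C10 non-endogenous; each day its own period, no wash-out stated | zero | missing (second condition fails) |
| C10 non-endogenous; Days 1 to 3 one period | zero | missing once Day 1 has given a quantifiable value (third condition fails) |
| C10 non-endogenous; one period, but the first quantifiable value reset each day | zero | zero |

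The last row needs a mixed reading that the SAP does not state.

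**Step 2: size of the added area.** Let L be the LLOQ, t1 the first postdose time, tp the last BQL time in the lag, and tf and Cf the time and value of the first quantifiable sample. With predose at L/2:

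- lag missing: area to tf = tf × (L/2 + Cf)/2
- lag zero: area to tf = t1 × L/4 + (tf − tp) × Cf/2
- difference = tp × Cf/2 + (tf − t1) × L/4

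The difference is driven by the lag (tp) and by how high the first quantifiable sample is (Cf).

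**Step 3: an invented record on the Day 3 times.** L = 2; BQL to 2.5 h; then 300, 500, 250, 125, 31, 16, 8, 2 at 3, 4, 5, 6, 8, 9, 10, 12 h.

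- Lag missing, 0 to 3 h: 3 × (1 + 300)/2 = 451.5
- Lag zero, 0 to 3 h: 0.5 × 1/2 + 0.5 × 300/2 = 75.25
- 3 to 12 h, the same in both: 400 + 360.7 + 180.3 + 134.8 + 22.7 + 11.5 + 8.7 = 1118.7
- Totals: 1570 against 1194, or +32%

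If the 3 h value is 30 instead of 300, the totals are about 1030 and 991, or about +4%. The result depends heavily on where the first quantifiable sample falls on the rising limb.

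**Step 4: range over assumed kinetics.** The documents give no lag, half-life, absorption rate or LLOQ for C10, so there is no figure of theirs to reproduce. Assumed: one compartment, half-life 0.5 to 3 h, ka 1.5 to 6 per h, LLOQ 1% or 5% of Cmax, no C10 background, and a 24 h sample closing each grid. Profiles that fail the SAP's minimum for computing an AUC are dropped. Error against the true modelled AUC on the Day 1/3 grid:

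| Lag (h) | Lag missing: range (median) | Lag zero: range |
|---|---|---|
| 1 | +5 to +28% (13%) | -18 to -1% |
| 1.5 | +8 to +48% (20%) | -17 to -1% |
| 2 | +10 to +73% (28%) | -18 to -1% |
| 2.5 | +13 to +91% (35%) | -18 to -2% |
| 3 | +21 to +61% (34%) | -46 to -3% |
| 4 | +28 to +80% (48%) | -33 to -3% |
| 5 | +35 to +102% (63%) | -34 to -5% |

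With a lag of 0.25 h no postdose sample is BQL before the first quantifiable one, and the two rules agree. On the Day 2 grid, for lags of 1 to 5 h, the missing rule runs from -23 to +57% and the zero rule from -46 to +6%. At the longest lags few Day 2 profiles meet the minimum for an AUC at all.

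**Step 5: accumulation ratio.** If Day 1 lag samples are zeroed and Day 3 lag samples are missing (rows two and three of the first table), two identical true profiles of the Step 3 kind give 1570/1194, an R_A of about 1.3 with no accumulation.

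**The case against.** The strongest reply is that the SAP can be read so that nothing goes wrong. It uses profile day and dosing interval for daily units and keeps dose period for something paired with a wash-out. In a parallel design with one three-dose treatment, Days 1 to 3 could all be the initial period, and the third condition could be applied profile by profile. If C10 is also non-endogenous, every lag sample is zero. The half-LLOQ and baseline bullets do not settle the class of C10, because they apply equally to SNAC. This shows that the problem is conditional. It does not remove it: the harmless outcome needs C10 to be non-endogenous and also needs either the mixed reading or a 24 h interval counted as wash-out, and the SAP states none of these.

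Two limits on frequency and visibility also stand. Where background C10 is quantifiable, the lag samples are quantifiable too and the error does not arise; no document gives the background or the LLOQ. Observed C10 profiles will be plotted and special data handling must be reported, so a reader could see the lag.

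A reader might infer more than the documents support:

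- That lag samples are missing on every day. Day 1 depends on an unstated class for C10.
- That a fixed inflation, such as 10 to 120%, is established. Any such range comes from assumed kinetics. Measured against zero-setting instead of the truth, the Day 1/3 scenarios with a lag BQL sample run from +2 to +199% (median +37%), partly because zero-setting itself reads low.
- That C10 AUC is always overstated. On Day 2 the sign varies.
- That the capsule-versus-tablet comparison is biased. SAP 10.3.2 models only LY3493269, C10 AUC is only summarised descriptively, and no contrast of C10 with SNAC is planned. C10 Cmax and tmax are unchanged.

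**Conclusion.** The gap is real and of low severity. No rule covers postdose BQL samples of C10 or SNAC before the first quantifiable postdose value, so the general rule applies. Under both literal readings it makes them missing on Days 2 and 3, and on Day 1 as well if C10 is endogenous. On the Day 1/3 grid the affected AUCs are too high, by an amount that the documents cannot fix. The +5 to +102% for lags of 1 to 5 h is illustrative and rests on the kinetics listed in Step 4. R_A for C10 is inflated only if Days 1 and 3 are handled differently. The primary LY3493269 comparison is not touched.

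**What to change.** In the C10 and SNAC bullets of SAP 10.3.1, state whether C10 is treated as endogenous and add: *On each profile day, postdose BQL concentrations before the first quantifiable postdose concentration of that day are set to zero.* Keep missing for BQL values that lie after that sample or at the end of the profile. Written by profile day, the sentence also removes the dependence on how dose period is read.

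The cost is this text and the BQL flag in the noncompartmental input. No new data are needed, and affected C10 AUCs become lower.

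Zero-setting is not exact. In a simulation with half-lives of 0.5 to 2 h, ka of 1.5 to 4 per h and LLOQ at 1% of Cmax, it recovered 92 to 97% of the true AUC on the Day 1/3 grid. The wider scenarios in Step 4 show larger shortfalls where sampling is coarse, down to -46% at worst. The advantage is that this error is confined to the single sampling interval in which C10 first appears, whereas the missing rule spreads it over the whole lag.

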**Data Monitoring Committee: No**

## 1.2. Schema

**Figure GZHI.1.1      Illustration of Parts A and B for Protocol J1X-MC-GZHI.**

### 1.3. Schedule of Activities (SoA)

#### Schedule of activities for Parts A and B

Study Activities	Screen	Study Period (Parts A and B)										Follow-up			Comments/Notes	
		CRU Inpatient Stay					Outpatient					Outpatient				
		-28 to -2	-1	1	2	3	4	5	6	8	15 ±1	29 ±3	43 ±3	ET		
Informed consent	X															
Medical history	X															
Physical examination	X															
Medical assessment			P	P	P		X	X	X	X	X	X	X	X	Medical review and symptom-directed physical examination, as appropriate.	
Height and weight	X		P		X				X	X	X	X	X	X	Height at screening only.	
Admit to CRU		X														
Discharge from CRU							X								At the investigator's discretion, participants may remain inpatient after Day 5.	
Outpatient visit to CRU								X	X	X	X	X	X	X		
Administer study drug			X	X	X										Refer to Section 6.1 for details	
AEs/concomitant medications	X	X	X	X	X	X	X	X	X	X	X	X	X	X		
ECG – single (h)	X		P, 1, 4, 12	P, 1, 4, 12	P, 1, 4, 12					X	X	X	X		ECGs must be recorded approximately within 30 minutes before collection of any blood samples (applicable for study visits).	
Vital signs: supine BP/PR (h)	X		P, 1, 4, 12	P, 1, 4, 12	P, 1, 4, 12	X	X	X	X	X	X	X	X			
Body temperature	X		P	P	P											
Clinical laboratory tests (fasted)	X		P				X		X	X	X	X	X		See Appendix 2 for details.	
Point-of-care safety glucose samples (glucose analyzer)			Days 1 – 4: Pre-meals (breakfast, lunch, and dinner) and before bedtime					X	X						Day 5: Fasted sample collected before breakfast.	

Study Activities	Scr n	Study Period (Parts A and B)									Follow-up			Comments/Notes
		CRU Inpatient Stay					Outpatient				Outpatient			
Days	-28 to -2	-1	1	2	3	4	5	6	8	15 ±1	29 ±3	43 ±3	ET	
LY3493269 PK sampling (h)		P, 0.5, 1, 1.5, 2, 2.5, 3, 4, 5, 6, 8, 9, 10, 12, 14	P, 1, 2, 3, 4, 8, 14	P, 0.5, 1, 1.5, 2, 2.5, 3, 4, 5, 6, 8, 9, 10, 12, 14	X	X	X	X	X	X	X	X	X	Days 15, 29, 43, and ET: Samples collected anytime during visit.
SNAC (Reference Formulation) or C10 (Test Formulations) PK sampling (h)		P, 0.5, 1, 1.5, 2, 2.5, 3, 4, 5, 6, 8, 9, 10, 12, 14	P, 1, 2, 3, 4, 8, 14	P, 0.5, 1, 1.5, 2, 2.5, 3, 4, 5, 6, 8, 9, 10, 12, 14	X	X								
Immunogenicity		P							X	X	X	X	X	Day 1: Samples are collected within 30 min of the predose PK samples.
Pharmacogenetic sample		X												Obtained any time on Day 1.

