### **10.3 Pharmacokinetic Assessment**

#### **10.3.1 Pharmacokinetic Analysis**

Noncompartmental methods applied with a validated software program (Phoenix WinNonlin v8.3.5) to the plasma concentrations of LY3493269, SNAC, and C10 will be used to determine the following PK parameters in Parts A and B, when possible:

### Profile Day 1

Parameter	Units	Definition
AUC(0-t last )	ng.h/mL	area under the concentration versus time curve from time zero to time t, where t is the last time point with a measurable concentration
AUC τ	ng.h/mL	area under the concentration versus time curve during one dosing interval
C max	ng/mL	maximum observed drug concentration
t max	h	time of maximum observed drug concentration
t last	h	time of the last quantifiable concentration

### Profile Day 2

Parameter	Units	Definition
AUC(0-t last )	ng.h/mL	area under the concentration versus time curve from time zero to time t, where t is the last time point with a measurable concentration
AUC τ,day 2	ng.h/mL	area under the concentration versus time curve during one dosing interval at day 2
C max,day 2	ng/mL	maximum observed drug concentration
t max,day 2	h	time of maximum observed drug concentration
t last	h	time of the last quantifiable concentration

### Profile Day 3

Parameter	Units	Definition
AUC(0-t last )	ng.h/mL	area under the concentration versus time curve from time zero to time t, where t is the last time point with a measurable concentration
AUC τ,day 3	ng.h/mL	area under the concentration versus time curve during one dosing interval at day 3
AUC(0-∞)	ng.h/mL	area under the concentration versus time curve from time zero to infinity
%AUC(t last -∞)	%	percentage of AUC(0-∞) extrapolated
C max,day 3	ng/mL	maximum observed drug concentration
t max,day 3	h	time of maximum observed drug concentration
t last	h	time of the last quantifiable concentration
t ½	h	half-life associated with the terminal rate constant (λz) in non-compartmental analysis
CL/F	L/h	apparent total body clearance of drug calculated after extra-vascular administration
V Z/F	L	apparent volume of distribution during the terminal phase after extra-vascular administration
V ss/F	L	apparent volume of distribution at steady state after extra-vascular administration

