R A	none	accumulation ratio (based on AUC τ on Profile Days 1 and 3)
F Rel	%	relative bioavailability of the test formulation compared to reference formulation (based on AUC[0-∞])
F Abs	%	absolute bioavailability of each oral treatment compared to an intravenous formulation (based on dose-normalized [DN] AUC[0-∞]):
$F_{Abs} = \frac{\text{Oral DN}^a \text{ AUC}(0 - \infty)}{\text{IV}^b \text{ DN AUC}(0 - \infty)} \times 100$		

a derived by dividing by the total oral dose administered (12)

b obtained from study J1X-MC-GZHA, using the geometric mean AUC(0-∞) of CCI LY3493269 IV

Additional PK parameters may be calculated, as appropriate. The software and version used for the final analyses will be specified in the clinical study report. Any exceptions or special handling of data will be clearly documented within the final study report.

Formatting of tables, figures and abbreviations will follow the Eli Lilly Global PK/PD/TS Tool: NON-COMPARTMENTAL PHARMACOKINETIC STYLE GUIDE. The version of the tool effective at the time of PK analysis will be followed.

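### The SNAC/C10 predose subtraction does not separate background from carry-over; where a Day 2 or Day 3 predose is quantifiable carry-over, that day's AUC is biased low and the expected accumulation ratio falls below 1

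*SAP*

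**What the plan says.** SAP section 10.3.1 applies noncompartmental methods "to the plasma concentrations of LY3493269, SNAC, and C10 will be used to determine the following PK parameters". The list that follows includes AUCτ on each profile day. For Day 3 it adds AUC(0-∞), half-life and an accumulation ratio R_A based on AUCτ "on Profile Days 1 and 3".

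Under Individual PK Parameter Rules there is a separate block for C10 and SNAC:

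- The correction is triggered day by day: "If quantifiable predose concentrations are observed for any of the PK profile days", the postdose values of those days are adjusted before parameters are calculated.
- The adjustment is a constant: "Baseline-adjustment will be performed by subtracting the PK profile day's quantifiable predose concentration from each postdose concentration belonging to that same PK profile day".
- A predose below the limit does not trigger it: "Predose concentrations that are BLQ will be set to half the LLOQ".

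For other samples below the limit, including late ones, the same section says "All other BQL concentrations that do not meet the above criteria will be set to missing".

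The General PK Parameter Rules use the logarithmic trapezoid after tmax. Neither set of rules says what to do with an adjusted concentration that is zero or negative. The SNAC/C10 plots use observed, unadjusted concentrations.

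**The concern.** Constant subtraction suits a constant background. Only the Day 1 predose is certain to contain no study-derived enhancer. A quantifiable predose on Day 2 or Day 3 may be what remains of the previous day's dose, and that remainder keeps falling during the next 24 hours. Subtracting its starting height from every later sample removes more area than the carry-over contributed.

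R_A is the parameter most exposed, because it exists to show carry-over and the rule takes more than the carry-over out of its numerator. A reader of the tables could conclude that an enhancer does not accumulate, or declines, when it accumulates. The Day 2 subtraction lowers Day 2 AUC but does not enter R_A, which uses Days 1 and 3 only.

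**Working it through.** The documents state no half-life, quantification limit, background level or accumulation ratio for SNAC or C10, so there is no figure to reproduce. The check asks what the rule does to a known profile.

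**Inputs from the documents.** Three once-daily doses (protocol section 4.1), so τ = 24 h. Sampling on Days 1 and 3 at predose, 0.5, 1, 1.5, 2, 2.5, 3, 4, 5, 6, 8, 9, 10, 12 and 14 h (protocol section 1.3). Two further SNAC/C10 samples are read as Day 4 and Day 5, about 24 and 48 h after the third dose. AUC is linear up to tmax and logarithmic afterwards (SAP 10.3.1).

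**Assumptions.** Linear one-compartment kinetics, equal doses, a quantifiable Day 3 predose that is entirely carry-over, and half-lives of 2 to 8 h.

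**Step 1: closed form for instantaneous absorption.** Let k = ln 2 / t½ and r = exp(−24k).

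- Day 3 predose = C0(r + r²)
- True R_A = 1 + r + r²
- Area removed ÷ true carry-over area = 24k / (1 − r)
- Adjusted R_A = 1 + (r + r²)[1 − 24k/(1 − r)]

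Since 24k > 1 − r for any k > 0, the bracket is negative and adjusted R_A is below 1 at every half-life. For example, at 6 h: r = 1/16, r + r² = 0.0664, 24k = 2.773 and 24k/(1 − r) = 2.773/0.9375 = 2.96. Adjusted R_A = 1 − 0.0664 × 1.96 = 0.87, against a true 1.07.

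**Step 2: the protocol's sampling times and the SAP's trapezoid, with first-order absorption (assumed ka = 1.5/h).**

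| Assumed t½ | Area removed ÷ true carry-over | Adjusted R_A, closed form | True R_A, sampled | Adjusted R_A, sampled |
|---|---|---|---|---|
| 2 h | 8.3 | 1.00 | 1.00 | 0.99 |
| 4 h | 4.2 | 0.95 | 1.02 | 0.90 |
| 6 h | 3.0 | 0.87 | 1.07 | 0.81 |
| 8 h | 2.4 | 0.81 | 1.15 | 0.75 |

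With ka = 2/h the adjusted sampled ratios are 0.99, 0.91, 0.81 and 0.75, so the result hardly depends on ka. The sampled ratios lie below the closed form largely because the adjusted 24 h value is close to zero (about 0.0003 of Cmax at 6 h). The log trapezoid from 14 to 24 h then understates the area.

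**Step 3: negative values.** With equal doses the adjusted value is C0·r³ at 24 h, which is positive, and C0(r³ + r⁴ − r) at 48 h. The latter is negative when r² + r³ < 1, that is r < 0.755 or t½ below about 59 h. It exists only if the raw 48 h sample is quantifiable, because otherwise it is set to missing. Raw 48 h ÷ predose = r(1 + r + r²)/(1 + r), which gives 1.6%, 6.3% and 12.7% at 4, 6 and 8 h. The predose must therefore exceed about 64, 16 and 8 times the quantification limit before a negative value can arise.

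**Step 4: unequal absorption between doses.** With an assumed between-dose CV of 30% to 100%, half-lives of 4 to 24 h and ka = 2/h, adjusted R_A is below 1 in about 53% to 78% of simulated participants. Its median is 0.55 to 0.93. The 24 h value is negative in about 23% to 52%, before any rule for values below the limit.

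**The case against.** The strongest reply is that the effect may never occur. If either enhancer clears within the day, the Day 2 and Day 3 predose is below the limit and nothing is subtracted. At a half-life of 2 h or less the ratio stays at 0.99 to 1.00. This stands: the bias is conditional, and the documents do not show whether the condition is met.

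Second, same-day subtraction is correct for a stable background. Protocol section 2.3 gives C10 food-additive status, so a dietary background is plausible. Participants are admitted on Day −1 and then eat unit meals, so a Day 1 predose may not represent later days. This stands for C10 and makes Day 1-only correction debatable.

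Third, SNAC/C10 pharmacokinetics is exploratory, its endpoints are AUC and Cmax rather than R_A, and the plots would show residual enhancer. That limits the weight of the point, but unadjusted plots do not correct tabulated parameters.

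Three stronger readings are tempting and not supported:

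- A reader might infer that R_A always falls below 1 and that late Day 3 samples always turn negative. Both need quantifiable carry-over. The 48 h value also needs a quantifiable raw sample, and it lies outside AUCτ, so it cannot affect R_A.
- A reader might infer that a SNAC predose on Day 2 or 3 can only be study residue. Protocol section 2.3 says SNAC is also contained in a vitamin B12 medical food, and section 6.8 exempts vitamin supplements from the medication restriction. Carry-over is the likelier source, not the only one.
- A reader might infer that the formulation comparison is affected. The rule is confined to C10 and SNAC, and the mixed model in SAP 10.3.2 covers LY3493269 only.

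**Conclusion.** The point holds conditionally. Where a Day 2 or Day 3 predose is quantifiable because of carry-over, the rule biases that day's AUC low. Under linear kinetics with equal doses it also puts the expected R_A below 1 whatever the true accumulation. The shortfall is about 0.01 at an assumed half-life of 2 h, 0.12 at 4 h, 0.26 at 6 h and 0.40 at 8 h (true minus adjusted, from the table). It is nil when the predose is below the limit, and there is no bias when the predose is a stable background.

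The missing rule for adjusted values at or below zero is a separate gap. The logarithmic trapezoid required after tmax is undefined for them. The sizes rest on assumed half-lives, absorption rate and equal doses, none of which the documents supply. The consequence is confined to exploratory SNAC/C10 parameters.

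**What to change.** Amend the C10/SNAC block of SAP section 10.3.1:

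- **SNAC:** do not subtract the Day 2 and Day 3 predose; derive AUCτ and R_A from observed concentrations.
- **C10:** base R_A on unadjusted concentrations, or on concentrations corrected by the Day 1 predose only.
- **Both:** report unadjusted parameters beside any adjusted ones, and state how adjusted values at or below zero are handled in AUC and in the terminal slope.

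The cost is a few lines of text and a rerun of the noncompartmental analysis for two analytes. With Part B cancelled, this concerns C10 in Treatments A1 and A2 and SNAC in A3. The downside is small: Day 1-only correction does not remove day-to-day drift in dietary C10, but the side-by-side results would show it.
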